7.7 PREGNANCY

Female patients enrolled in the study should make every effort to avoid becoming pregnant during their participation in the study. Female patients should be reminded at every visit to use appropriate birth control methods. However, if a female patient should become pregnant during the study (i.e., from the date the ICF was signed until the patient's last visit), the investigator (or authorized delegate) should notify the designated safety contact and [REDACTED], Inc., on the initial Pregnancy Report form within 24 hours of the investigator (or authorized delegate) first becoming aware of the pregnancy. Pregnancy itself is not an AE, unless there is suspicion that the investigational product may have interfered with the effectiveness of a contraceptive medication. Pregnancy reports, however, are tracked and reported in the safety (SAE) database but will be reported separately from SAEs. Pregnancy occurring in the patient between the date the ICF was signed until 30 days after the last dose of study medication will fall under the expedited reporting procedure for serious adverse events. The pregnant patient will be immediately discontinued from the study but will be followed for the duration of the pregnancy. Details of the outcome of the pregnancy (e.g., full term normal delivery, stillbirth, congenital anomalies, or miscarriage) will be collected and reported by the site.

All reports of congenital abnormalities/birth defects are SAEs. Spontaneous miscarriages should also be reported and handled as SAEs. However, elective abortion without complications should not be handled as SAEs.

All outcomes of pregnancy, if known, must be reported by the Investigator to the Medical Monitor or designated safety contact on the pregnancy outcome report form within 30 days after he/she has gained knowledge of the facts. See **Section 11, Appendix B** for additional details on pregnancy reporting requirements.

8. STATISTICAL METHODS

The objectives of the study are to assess the safety and efficacy of plecanatide 0.5, 1.0, 2.0 and 3.0 mg dosed daily, compared with placebo.

Before database lock and un-blinding, a formal statistical analysis plan (SAP) will be written and will include details of all statistical methods to be used to analyze the efficacy and safety data. The SAP will supersede the protocol with respect to the analyses specified, although the primary analysis described in this section will remain unchanged.

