8.4 GENERAL CONSIDERATIONS

The final data analysis will be performed after all patients have either completed or have been discontinued from the study. The study will be unblinded after patient membership in each of the various analysis populations has been determined at a blinded data review meeting and upon confirmation of database lock.

Three treatment groups are identified for all analyses cited in the following as “by treatment group”: A (patients in Age Group A receiving plecanatide doses of 0.5 mg or 1.0 mg); B (patients in Age Group B receiving plecanatide doses of 1.0 mg, 2.0 mg, or 3.0 mg); Placebo (all patients randomized to receive placebo.)

Any deviations from the analyses presented here will be detailed in the clinical study report. All outputs will be produced using SAS® version 9.2 or later.

All efficacy data will be summarized and analyzed using the FAS and PP Populations unless otherwise noted. Safety data will be summarized using the Safety Population.

Imputation of missing data, where appropriate, will be performed as indicated for a given analysis. Any spurious or erroneous data will be queried and followed up until satisfactorily resolved; if not resolvable, the data will be set to missing. All data collected in the clinical database will be included in the data listings.

Summary statistics—number of patients (n), mean, standard deviation (SD), median, minimum, and maximum—will be presented for continuous variables. Frequencies and percentages will be presented for categorical variables. Unless otherwise noted, percentages will be calculated using the total number of patients in the appropriate population and/or subgroup and per treatment group where applicable. Where data are collected over time, both the observed data and change from the Screening Period (baseline) will be summarized at each time point.

Statistical testing including p-values and confidence intervals (CIs) will be presented as described in each section below. The Type I error rate (alpha) for the analysis of the primary efficacy endpoint is 0.05 (two-sided).

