8.8.1.1 Analysis of the Primary Efficacy Endpoint

The weekly SBM rate for each patient will be computed, as described in **Section 8.4.1**, for each week of the 4-week treatment period. The change from baseline in mean weekly SBM rate will be analyzed using a linear mixed-effects model with fixed effects for gender (stratification variable), treatment, week, and the corresponding baseline value; a random intercept for patient will also be specified. The least squares (LS) mean change from baseline will be presented, by treatment group, and the difference in LS means for each treatment group, A, B, and A and B combined, versus Placebo, with 95% confidence intervals and corresponding statistical *p*-values.

The above analysis will be repeated for the PP Population.

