5.2.2. Primary Efficacy Analysis

The weekly SBM rate for each subject will be computed for each week of the 4-week treatment period. The change from baseline in mean weekly SBM rate will be analyzed using a linear mixed-effects model with fixed effects for gender (stratification variable), treatment, week, the interaction of treatment and week, and the corresponding baseline value; a random intercept for subject will also be specified. The least squares (LS) mean change from baseline will be presented, by treatment groups, and the difference in LS means for each treatment group versus placebo and combined active doses within each age group versus placebo in a separate model for each age group, and overall active doses versus placebo in a separate model with 95% confidence intervals and corresponding statistical p-values.

The baseline SBM weekly rate will be the weekly average number of SBMs recorded during each of the 2 weeks preceding initiation of study drug.

The above analysis will be repeated for the PP Population.

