7. CHANGES IN THE PLANNED ANALYSES

In accordance with the FDA guidance (FDA Guidance on Conduct of Clinical Trials of Medical Products during COVID-19 Pandemic, March 2020), processes were put in place to ensure that any impacted study assessments can be identified in the study database. Any impacted assessments for subjects participating in this study will be identified in the relevant individual subject listings. Any subject discontinued due to COVID-19 disruption, will be noted as such in the subject disposition summary and associated individual subject listing.

SAP Version 2.0 changes: For the Per Protocol population, the compliance threshold for eDiary was updated to eDiary compliance of at least 70% instead of at least 80%. Overall, this eDiary compliance threshold is considered adequate in this pediatric subject population and in the context of the COVID-19 pandemic.

The Per Protocol population was also updated to expand visit windowing for Visit 3/Week 4 from the protocol-specified window of 28 +3 days. to 28 days plus or minus 3 days. Protocol-specified visit window is 28 to 31 days, however it is expected that a subject with Week 4 completed in the 25 to 31 day window, with adequate treatment compliance and diary compliance as specified for the PP Population, is reflective of 4 weeks of study treatment, as intended by the study objectives.

Clarification was added for the pharmacokinetic analyses, utilizing actual sampling times for PK parameter estimation, and also to state the definitions for Cmax, Tmax, and Cmin.

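### The protocol locks a primary analysis that compares each age group's treated patients with placebo patients of both ages; the SAP replaces it with a sounder within-age comparison but does not record the change

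*Combined protocol and SAP*

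**What the plan says.** Protocol section 8 lets the SAP override the protocol on analyses with one exception: "The SAP will supersede the protocol with respect to the analyses specified, although the primary analysis described in this section will remain unchanged".

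The protected analysis is set out in three places. Protocol 8.4 begins "Three treatment groups are identified for all analyses cited in the following" and defines them as A (children on either dose), B (adolescents on any of three doses) and "Placebo (all patients randomized to receive placebo". Protocol 8.8.1.1 gives the model: "fixed effects for gender (stratification variable), treatment, week, and the corresponding baseline value; a random intercept for patient will also be specified". It has no term for age group. The same section asks for "the difference in LS means for each treatment group, A, B, and A and B combined, versus Placebo". The synopsis repeats the model and contrasts.

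The SAP differs. Section 5 lists seven age/dose groups, with a separate placebo column inside each age group. Section 5.2.2 asks for each dose versus placebo and "combined active doses within each age group versus placebo in a separate model for each age group", plus one overall active-versus-placebo model. It adds a treatment-by-week term, and section 5 selects the covariance structure by model fit.

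SAP section 7, on changes in the planned analyses, covers COVID-19 handling, two per-protocol population changes ("SAP Version 2.0 changes: For the Per Protocol population, the compliance threshold for eDiary was updated", and the Week 4 window) and a pharmacokinetic clarification. It does not mention the primary analysis.

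**The concern.** Two different primary analyses are written down, and the lock clause favours the less sound one. Patients are randomized within age group, 1:1:1 in children and 1:1:1:1 in adolescents, so randomization protects a comparison of treated children with placebo children. It does not protect a comparison of treated children with a placebo group that is half adolescents. With no age term, any age difference in placebo response enters the A and B contrasts as if it were a drug effect.

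The documents give reasons not to assume that this difference is zero. The sample-size text regards adult data as more applicable to the adolescents. SAP 3.3.7 expects parental oversight of the diary for the younger group, while adolescents may complete it themselves. Protocol 3.3.1 sets rescue laxative amounts by age, and rescue use decides whether a bowel movement counts as spontaneous.

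At stake is which estimate and p-value count as the primary result for each age group, and whether the change of comparator can be shown to have been made before unblinding.

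**Working it through.** **Inputs.** Planned arm size 30 (protocol Table 3), so A active = 60, B active = 90 and pooled placebo = 30 + 30 = 60. Difference 1.5 SBM per week, SD 2.3 on placebo and 3.5 on plecanatide (protocol 8.2). Two-sided alpha 0.05 (protocol 8.4).

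**Reproducing the plan's own figure.** For 102 versus 34:

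SE = √(2.3²/34 + 3.5²/102) = 0.525; power = Φ(1.5/0.525 − 1.96) = 81.5%.

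This matches the stated 81.5% at a two-sided level of 0.05. It does not match at the printed 0.05%, which would give 26.6%; that is a separate matter.

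**Bias.** Let d = mean change on placebo in children minus that in adolescents. With no drug effect:

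- A minus pooled placebo = child mean − (½ child mean + ½ adolescent mean) = +0.5d
- B minus pooled placebo = adolescent mean − (½ child mean + ½ adolescent mean) = −0.5d

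The signs are opposite, so the same d flatters one age group and penalizes the other.

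**Type I error.** Normal approximation, counting rejections in either direction:

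SE = √[(2.3² + (d/2)²)/60 + s²/n], with n = 60 for A and 90 for B;

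error = 1 − Φ(1.96 − 0.5d/SE) + Φ(−1.96 − 0.5d/SE).

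The active SD s is taken as 3.5 (the plan's figure) and as 2.3 (the natural choice if the drug does nothing). The term (d/2)² is the spread added by mixing two ages in the placebo group. Example for A, d = 0.5, s = 3.5: SE = √(5.3525/60 + 12.25/60) = 0.542; 0.25/0.542 = 0.462; error = 0.067 + 0.008 = 7.5%.

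| Assumed d (SBM/week) | Size of bias | Share of 1.5 | A: s = 3.5 to 2.3 | B: s = 3.5 to 2.3 |
|---|---|---|---|---|
| 0 | 0 | 0% | 5% | 5% |
| 0.25 | 0.125 | 8% | about 6% | about 6% |
| 0.5 | 0.25 | 17% | 7.5% to 9% | 8% to 10% |
| 1.0 | 0.50 | 33% | 15% to 22% | 18% to 25% |

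**Power under each comparator**, at the plan's difference and SDs:

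| Contrast | Pooled placebo (60) | Same-age placebo (30) |
|---|---|---|
| A combined (60 active) | SE 0.541, 79% | SE 0.617, 68% |
| B combined (90 active) | SE 0.474, 89% | SE 0.559, 77% |

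These figures ignore covariate adjustment and dropout.

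**The case against.** Three arguments carry weight.

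First, a reader might infer that the trial will report two competing sets of primary estimates. The SAP does not support that. Its section 5 comparisons are within A, within B and overall; its primary-endpoint tables in 9.1 are produced by age group; and it contains no contrast of A or B against all placebo patients. The age-mixed contrast would be run only if someone returned to the protocol text. The lock clause nevertheless gives a formal reason to do so.

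Second, a reader might call the change an undeclared departure. That goes too far. Protocol 8.4 says deviations from its analyses will be detailed in the clinical study report, and part of SAP section 7 is explicitly a log of changes in SAP version 2.0. But section 7 also records a departure from a window that it describes as protocol-specified, so departures from the protocol do belong there and this one is missing. A later statement in the study report would not reconcile the lock clause with the SAP.

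Third, the added treatment-by-week term might look like a material change. It is close to immaterial. Both documents set weeks with no bowel-movement record to zero, so every patient contributes four weekly values. With complete, balanced weeks and a random intercept, the four-week average contrast is the same with or without the interaction. The change that matters is in the groups and the comparator.

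It is also fair to say that much is retained: the endpoint, the full analysis set, the gender and baseline covariates, the random intercept and an overall contrast.

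**Conclusion.** The point holds as a should-fix. The protocol contains a locked primary rule whose A and B contrasts mix drug effect with age by ±0.5d, and the SAP contradicts that rule without recording the change. The SAP's direction is right; the fault lies in the unreconciled clause and the missing record.

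The size depends on d, which the documents do not give. If d = 0 there is no bias. At 0.5 SBM per week the bias is 0.25, or 17% of the planned effect; at 1.0 it is a third. The type I figures are upper guides because the baseline SBM covariate may absorb part of d. They also assume that the plan's adult SDs apply to the four-week average, so the highest values should not be read as the expected error rate.

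The overall contrast is a lesser matter. Active patients are 60/150 = 40% children against 50% of placebo, so simple pooling gives a bias of −0.1d.

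A higher grade is not warranted: the within-age analysis is already the scheduled one, and the trial is an exploratory phase 2 study.

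**What to change.** Before unblinding:

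1. Amend the synopsis, protocol 8.4 and protocol 8.8.1.1 so that A and B are each compared with placebo patients of the same age group, as in SAP 5.2.2. Drop the contrasts of A and of B against all placebo patients.
2. Update the clause in protocol section 8 so that it no longer protects the replaced analysis.
3. Add an entry to SAP section 7 recording the change of groups, comparator and covariance rule, with the reason and the date relative to unblinding. The treatment-by-week term can be noted in the same entry.

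The cost is a short amendment and one SAP entry; no data collection changes. The statistical price is the smaller control group, 30 rather than 60 placebo patients per age-group contrast. Power for the combined doses is then about 68% rather than 79% in A and 77% rather than 89% in B, a loss that SAP 5.2.2 already accepts. The higher figures are not a real alternative, since the extra placebo patients come from the other age group.

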8.1 RANDOMIZATION AND TREATMENT ASSIGNMENT

This is a double-blind, placebo-controlled study with seven treatment age/dose groups that will be conducted at up to approximately 20 clinical sites. Approximately 210 patients (90 children and 120 adolescents) will be randomized to receive plecanatide or matching placebo. Patients 6-11 years of age will be randomly assigned to 1 of 3 treatment groups (2 active treatments, 1 matching placebo) in a 1:1:1 ratio and patients 12 to < 18 years of age will be randomly assigned to 1 of 4 treatment groups (3 active treatments, 1 matching placebo) in a 1:1:1:1 ratio using an Interactive Web-based Response System (IWRS).

Central, block randomization will be performed with stratification by gender.

8.2 SAMPLE SIZE AND POWER CONSIDERATIONS

Based on data from two phase 3 trials conducted by the sponsor in adults with IBS-C, consider the sample size necessary for observing a significant difference in the change from baseline in SBM frequency in Group B (the adolescents) since data from the adults is likely more applicable to Group B participants. Then, a study with a plecanatide group sample size of 102 and a placebo group sample size of 34 (representing 3:1 randomization, plecanatide to placebo) achieves 81.5% power at the 0.05% level of significance when the difference in mean change from baseline in weekly SBM frequency at four weeks is 1.5 and the placebo group and plecanatide group standard deviations are 2.3 and 3.5 respectively. Since study SP304202-14 is being conducted in children and adolescents with IBS-C, and the primary analysis of the primary endpoint will be an ANCOVA using a linear mixed-effects model, the sponsor believes that 30 patients per treatment group (placebo and 3 dose levels of plecanatide), yielding a planned target enrollment of a total of 210 patients (90 children and 120 adolescents), will prove sufficient for achieving the primary objective of this phase 2 study.

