	
Based on data from two phase 3 trials conducted by the sponsor in adults with IBS-C, consider the sample size necessary for observing a significant difference in the change from baseline in SBM frequency in Group B (the adolescents) since data from the adults is likely more applicable to Group B participants. Then, a study with a plecanatide group sample size of 102 and a placebo group sample size of 34 (representing 3:1 randomization, plecanatide to placebo) achieves 81.5% power at the 0.05% level of significance when the difference in mean change from baseline in weekly SBM frequency at four weeks is 1.5 and the placebo group and plecanatide group standard deviations are 2.3 and 3.5 respectively. Since study SP304202-14 is being conducted in children and adolescents with IBS-C, and the primary analysis of the primary endpoint will be an ANCOVA using a linear mixed-effects model, the sponsor believes that 30 patients per treatment group (placebo and 4 dose levels of plecanatide), yielding a planned target enrollment of a total of 210 patients (90 children and 120 adolescents), will prove sufficient for achieving the primary objective of this phase 2 study.
 
Analysis Populations
 
Analysis populations include the Full Analysis Set (FAS), the Per Protocol (PP) population, and the Safety Population (SP). The FAS will include all randomized and treated patients who had the baseline assessment and at least one post randomization assessment of the primary efficacy measure of weekly SBM frequency. The FAS will be the primary population for efficacy analyses. The SP will include all patients who were randomly assigned to a treatment group and received at least 1 dose of study drug.
 
Patient Characteristics and Disposition
 
Demographic characteristics (including age, gender, race, weight, height, and body mass index) and characteristics of patient's IBS history will be summarized by descriptive statistics for each treatment group.
 
Efficacy Analyses
 
• Primary Efficacy Analysis 
The weekly SBM rate for each patient will be computed for each week of the 4-week treatment period. The change from baseline in mean weekly SBM rate will be analyzed using a linear mixed-effects model with fixed effects for gender (stratification variable), treatment, week, and the corresponding baseline value; a random intercept for patient will also be specified. The least squares (LS) mean change from baseline will be presented, by treatment group, and the difference in LS means for each treatment group, A, B, and A and B combined, versus Placebo, with 95% confidence intervals and corresponding statistical p-values.
 
The above analysis will be repeated for the PP Population.
 
• Secondary Efficacy Analysis 
The mean in each period and the change from baseline will be summarized in each treatment group. Differences between treatment groups will be analyzed with an analysis of covariance, including fixed effects for gender (stratification variable) and treatment and corresponding baseline value as a covariate. A least

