8.8 EFFICACY ANALYSES

8.8.1 Primary Efficacy Endpoint

The primary efficacy endpoint is the change from baseline in weekly SBM rate over the 4-week treatment period.

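### The only stated power, 81.5% at a printed level of 0.05%, holds at two-sided alpha 0.05 for 102 vs 34 adolescents; it is not the power of the planned 90 vs 30, and the model gain invoked to bridge the gap is not quantified

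*Combined protocol and SAP*

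**What the plan says.** The synopsis, protocol section 8.2 and SAP section 3.1 carry the same calculation. It uses adult phase 3 data, applied to Group B as the age group to which those data are more relevant. It takes "a plecanatide group sample size of 102 and a placebo group sample size of 34 (representing 3:1 randomization, plecanatide to placebo") and states that this "achieves 81.5% power at the 0.05% level of significance when the difference in mean change from baseline in weekly SBM frequency" takes its assumed value. The assumed "difference in mean change from baseline in weekly SBM frequency at four weeks is 1.5", with standard deviations of 2.3 on placebo and 3.5 on plecanatide.

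The next sentence moves to 30 patients per group. The reasons given are the study population and that "the primary analysis of the primary endpoint will be an ANCOVA using a linear mixed-effects model". No correlation, variance reduction or power accompanies that step. Protocol section 8.1 confirms the numbers: "Approximately 210 patients (90 children and 120 adolescents) will be randomized to receive plecanatide or matching placebo". With 1:1:1:1 allocation, the 120 adolescents divide into 90 on plecanatide and 30 on placebo.

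Protocol section 8.4 and SAP section 5 both set the primary alpha at 0.05, two-sided.

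The two documents differ on the comparator. Protocol section 8.8.1.1 plans "the difference in LS means for each treatment group, A, B, and A and B combined, versus Placebo", and section 8.4 defines Placebo as every patient randomized to placebo, which is 30 + 30 = 60. SAP section 5.2.2 instead fits a separate model in each age group, so Group B is compared with its own 30 placebo patients. Protocol section 8 lets the SAP supersede it on analyses but says that the primary analysis stays as the protocol describes it.

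**The concern.** A reader who takes the sample-size text at face value learns a power and an alpha that do not belong together, for a group size that will not be enrolled. The power of the comparison that will be made cannot be found in either document. Nor can a reader derive it, because the only argument for 30 rather than 34 per arm is a model whose gain is not given a value.

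The gain cannot be inferred from the inputs either. The assumed difference is described as at four weeks, whereas "The primary efficacy endpoint is the change from baseline in weekly SBM rate over the 4-week treatment period". The text does not say whether 3.5 and 2.3 are standard deviations for a single week or for a four-week average. How much repeated measurement can add depends on which they are.

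What is at stake is the sponsor's ability to interpret a null or borderline result in Group B. On the plan's own inputs, the comparator alone moves power by about 12 percentage points (88.6% minus 76.5%).

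**Working it through.** **Inputs, from protocol section 8.2.** Difference 1.5; SD 3.5 on plecanatide (variance 12.25); SD 2.3 on placebo (variance 5.29). Alpha is 0.05 two-sided, from protocol section 8.4 and SAP section 5. No dropout is applied, since the documents give no rate.

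**Method.** SE = √(12.25/n₁ + 5.29/n₀); power = Φ(1.5/SE − z), with z = 1.96 at two-sided 0.05 and z = 3.48 at two-sided 0.0005. The opposite tail is negligible.

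**Step 1: the plan's own figure.** For 102 vs 34, SE = √(0.1201 + 0.1556) = 0.525 and 1.5/SE = 2.857.
- Two-sided 0.05: Φ(0.897) = 81.5%. This matches. One-sided 0.025 is numerically the same test.
- Two-sided 0.05% (0.0005): Φ(−0.624) = 26.6%. This does not match; one-sided 0.05% gives 33.2%.
- One-sided 0.05 gives 88.7%, which also does not match.

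**Step 2: the planned numbers, same method and no model gain.**

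| Contrast | n | SE | 1.5/SE | Power |
|---|---|---|---|---|
| Group B combined vs Group B placebo (SAP 5.2.2) | 90 vs 30 | 0.559 | 2.684 | 76.5% |
| Group B combined vs pooled placebo (protocol 8.4, 8.8.1.1) | 90 vs 60 | 0.474 | 3.167 | 88.6% |

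Welch t versions are 75.5% and 88.2%. The second row assumes that the 30 children on placebo share both the SD of 2.3 and the adolescents' mean placebo change. If the children's mean differed by 0.5 SBM per week (an illustrative value), the pooled placebo mean would shift by 0.25. The detectable difference would become 1.25 or 1.75, and power about 75% or 96%.

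**Step 3: the gain needed.** Arm sizes of 90 and 30 are both 90/102 of the sizes in the power statement. Restoring 81.5% therefore needs residual variance multiplied by 90/102 = 0.882, a reduction of 11.8%. If this came only from baseline adjustment (variance × (1 − r²)), r = √0.118 ≈ 0.34 between baseline and change.

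**Step 4: plausible gain at 90 vs 30, on assumed values.**
- If the SDs are four-week averages, r of 0.3 to 0.5 gives 80.3% to 87.3%.
- If they are single-week SDs, averaging four weeks multiplies variance by (1 + 3ρ)/4. For a within-patient correlation ρ of 0.8 to 0.6 the factor is 0.85 to 0.70, and power is 82.9% to 89.4% before baseline adjustment.

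**Step 5: dependence on the variance model.** The figures above let the two arms have different variances. The planned mixed models state no treatment-specific variance. With a common variance at 90 vs 30, the pooled variance is (89 × 12.25 + 29 × 5.29)/118 = 10.54, so the model SE is √(10.54 × (1/90 + 1/30)) = 0.684. The critical difference is 1.980 × 0.684 = 1.355, and power is Φ((1.5 − 1.355)/0.559) ≈ 60%. At 90 vs 60 the pooled variance is 9.475, the model SE 0.513 and the critical difference 1.014, so power is Φ((1.5 − 1.014)/0.474) ≈ 85%. Simulation with 100,000 replicates agrees (60.4% and 84.7%). All of these are before any gain.

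**The case against.** The arithmetic behind 81.5% is sound once the level is read as 0.05, and the misprint has no operational effect: both documents set the primary alpha elsewhere. A reader might infer that the primary test will be run at 0.0005, with 26.6% power. Protocol section 8.4 and SAP section 5 rule that out.

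The move from 34 to 30 per arm is also disclosed, with a reason, in the sentence after the power figure. A modest gain from the model would close the gap, and under the protocol's pooled comparator there is no shortfall by the plan's own method. Both documents call the trial exploratory and make no multiplicity adjustment.

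Much of this stands, and it limits the point to documentation. It does not remove it. Disclosing a smaller number per arm with an unquantified reason does not give the power at that number, and 81.5% describes neither document's contrast.

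A reader might also point to the SAP's single-dose tests. A single Group B dose against Group B placebo (30 vs 30) has about 50% power, even if that dose has the full 1.5 difference. The documents claim no power for single doses, so this is context and not a failed promise.

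**Conclusion.** The power statement is wrong as written in two respects: its alpha is misprinted in three places, and its sample size is not the planned one. On the plan's inputs and by the method that reproduces 81.5%, the planned Group B combined contrast has 76.5% power with the SAP's comparator or 88.6% with the protocol's, before model gain. The second figure also carries adult and adolescent placebo assumptions over to children.

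It would be tempting to conclude that the trial is underpowered. The documents do not support that. An 11.8% variance reduction restores the quoted power at 90 vs 30, and such a gain is plausible, though it is not documented. The result also depends on the variance model: a common-variance analysis without gain would have about 60% or 85%, so any restated figure means little unless its method is named.

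The statement should be corrected. The arithmetic is certain; the size of the model gain is unknown.

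**What to change.** Keep enrolment as planned and make these changes in the synopsis, protocol section 8.2 and SAP section 3.1.

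1. Replace 0.05% with two-sided alpha 0.05.
2. Reconcile the comparator between protocol sections 8.4 and 8.8.1.1 and SAP section 5.2.2, taking account of the statement in protocol section 8 that the primary analysis remains unchanged.
3. Replace the 102 vs 34 figure with the power for the reconciled contrast, naming the unequal-variance normal approximation. That is 76.5% for 90 vs 30, or 88.6% for 90 vs 60. Label the latter as assuming that children on placebo share the adult SD of 2.3 and the adolescents' mean placebo change.
4. Either let the mixed model have treatment-specific variances, so that these figures apply, or print the common-variance power (about 60% at 90 vs 30, about 85% at 90 vs 60, before gain).
5. If a model gain is claimed, give the assumed variance reduction and say whether the SDs are for one week or a four-week average.

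A single-dose figure is optional.

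The cost is wording in three places, a comparator decision that is needed before analysis anyway, and one choice about the variance model. No patients are added and the endpoint does not change. The downside is that the stated power may fall below 81.5%.
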